5.1 Contraception requirements

Please refer to exclusion criteria ([Section 4](#)) for details of contraception requirements for the study.

[figure not shown]
5.2 Prohibited treatment

Obeticholic acid: 30 days prior to randomization, during treatment and until completion of the End of Study visit.

Investigational drugs: within 5 half-lives/30 days of randomization, whichever is longer; (or longer if required by local regulations).

Immunosuppressive drugs: within 30 days of randomization. Exception; the use of high dose oral steroids to treat co-morbid conditions (e.g. airways disease) will be allowed but must be properly documented as such in concomitant medications.

No medication or herbal remedies likely to have an impact on LJN452 metabolism will be allowed from the first dosing until day 28 (Part 1) or End of Study (Part 2) evaluations have been conducted.

A full list of prohibited medications will be provided in the SOM.

5.3 Dietary restrictions and smoking

- No alcohol consumption is allowed for 8 hours before dosing and each study visit until Study Completion evaluation.
- In Part 1: all subjects will fast (i.e., no food and liquid except water) for at least 8 hours prior to administration of study drug and will continue to fast for at least 2 hours thereafter. No fluid intake apart from the fluid given at the time of drug intake is allowed from 2 h before until 2 h after dosing.
- In Part 2: all patients will fast (i.e. no food and liquid except water) for at least 8 hours prior to each dose and should refrain from drinking for at least 30 min post dose, and refrain from eating for at least 60 min post dose. A light breakfast may be taken after 60 minutes.

5.4 General restrictions

- No strenuous physical exercise (e.g., weight training, aerobics, football) until after Study Completion evaluation.

Note: Patients should be reminded by site staff that on the day of a study visit during the treatment period to not take their study medication at home that morning, and to come fasted and bring their study medication with them to take once their pre-dose assessments have been completed.

6 Treatment

6.1 Study treatment

Details on the storage and management of study medication, randomization and instructions for prescribing and taking study treatment are outlined in Section 3 of the Site Operations Manual.

6.1.1 Investigational treatment

The investigational drug, LJN452 0.01 mg, 0.03 mg or 0.1 mg and matching placebo will be prepared and supplied by Novartis as a single blind patient specific packs to be dispensed by the unblinded pharmacist at the investigator site.

In Part 1, once a patient is confirmed as eligible after completion of their Baseline assessments, a Randomization Number can be requested, following the process in the Site Operations Manual. The Pharmacist/unblinded designee then dispenses the study medication according to the treatment assignment for that Randomization number, according to the supplied randomization schedule (provided via Treatment Allocation Cards or Electronic Randomization list).

In Part 2, once a patient is confirmed as eligible after completion of their Screening assessments, the site will contact the Interactive Response Technology (IRT) system, which will randomize the patient to the appropriate treatment. For further details, please see the Site Operations Manual and NIRT Site user manual.

6.2 Treatment arms

Part 1

Patients in each cohort will be assigned to one of the following treatment arms in a ratio of 2:1. The number of patients enrolled in Cohorts 2-5 may change based on data from IAs.

Cohort 1:

- LJN452 0.03 mg daily for 28 days (n=10) (given as 3 x LJN452 0.01 mg)
- LJN452 Placebo daily for 28 days (n=5)

Cohort 2:

- LJN452 0.06 mg daily for 28 days (n=10)
- LJN452 Placebo daily for 28 days (n=5)

Cohort 3:

- LJN452 0.09 mg daily for 28 days (n=10)
- LJN452 Placebo daily for 28 days (n=5)

Cohorts 4-5 (if required) may receive different doses:

- LJN452 TBD mg daily for 28 days (n=10)
- LJN452 Placebo daily for 28 days (n=5)

Part 2

Patients in Part 2 will be assigned to one of the following treatment arms in a ratio of 3:3:2.

- LJN452 Dose level 1: TBD [REDACTED]
daily for 12 weeks (n=33)
- LJN452 Dose level 2: TBD [REDACTED]
daily for 12 weeks (n=33)
- LJN452 Placebo daily for 12 weeks (n=22)

Part 2 dose levels will be selected based on a balance of safety, tolerability and efficacy.
The dose levels selected in Part 2 will be approved by the DMC and [REDACTED]
[REDACTED]

6.2.1 Permitted dose adjustments and interruptions of study treatment

Part 1

Within a cohort, once a dose is decided on, study drug dose adjustments are not permitted.
Interruption to study drug may occur based on the criteria outlined in [Table 15-1](#) (Liver events)
and [Table 6-1](#) (Pruritus event definitions and required actions).

In case of notable adverse events or safety concerns during dose escalation of the study, the following changes to the next planned dose level may be considered:

- Administration of a dose below the starting dose
- Administration of an intermediate dose between the current and preceding dose
- Administration of an intermediate dose between the current and next planned dose
- Repeated administration of the current dose
- Termination of any further dose escalation

These changes must be recorded on the Dosage Administration Record CRF.

Part 2: Option for dose reduction when ALT or AST > 2 x Baseline value AND $\leq 8 \times \text{ULN}$

For patients who experience ALT or AST elevations meeting the definitions outlined in [Table 15-1](#), a dose interruption or dose reduction to the next lower dose level, (or to placebo if receiving the lowest dose level) is permitted. One dose reduction step is allowed per patient. If, despite being on a reduced dose, a patient has persistent (i.e. remains $> 90\%$ of the original elevated level) or new ALT or AST elevation, they must be discontinued from study treatment. Increasing the dose to the original level is not permitted.

If the patient has symptoms or other LFTs are also elevated please refer to [Appendix 1](#) for appropriate actions.

Patients with AST or ALT values meeting the requirement will be instructed to return to the clinic for an additional visit, where repeat tests will be performed, including a physical examination and laboratory assessment including ALT, AST, GGT, alkaline phosphatase, total bilirubin, albumin and PT/INR.

The central laboratory should be used, if this is not possible, the repeats can be performed at a local laboratory to monitor the safety of the patient. If tests are performed at local laboratory, results will be captured in source documents only. In all cases, a physical examination should be performed and recorded in source documents.

Table 15-1 in [Appendix 1](#) outlines the required testing frequency and resultant actions dependent on the outcome of the repeat assessments.

If the additional laboratory evaluation confirms the increase of ALT and/or AST values, the study treatment will be reduced to the next dose level in a blinded manner ([Table 6-1](#)). The procedure for dose reduction is outlined in the Site Operations Manual.

If the additional laboratory evaluation does not confirm the significant increase of ALT values, the patient will continue with the assigned/original dose level.

If the additional laboratory evaluation shows a higher elevation of ALT and/or AST (e.g. $> 8 \times$ ULN) as compared to the original elevation (e.g. $> 5 \times$ ULN but $\leq 8 \times$ ULN), the guidance for this higher elevation (e.g. $> 8 \times$ ULN) should be followed.

Table 6-1 Part 2 Permitted dose reductions

Original treatment (daily dose)	Reduced treatment (daily dose)
Dose Level 1	Placebo
Dose Level 2	Dose Level 1
Placebo	Placebo

Repeat/second dose reductions are not permitted. Returning to the original treatment is not permitted.

Patients with a persistent or a second cycle of elevated ALT or AST while on the reduced dose will be instructed to return to the clinic for repeat tests as outlined in [Table 15-1](#). If the repeat tests confirm the elevated ALT or AST values, the patient will discontinue study treatment. If the repeat tests do not confirm elevation, the patient will continue with the reduced dose.

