ALT or AST > 3 x ULN and INR > 1.5	
 • Discontinue study drug • Hospitalize, if clinically appropriate • Establish causality and complete liver event checklist (in SOM) 	--	Continue monitoring with Repeat tests ^a until resolution ^c	--	--
ALT or AST > 8 x ULN	
 • Discontinue study drug • Hospitalize if clinically appropriate • Establish causality and complete liver event checklist (in SOM) 	--	Continue monitoring with Repeat tests ^a until resolution ^c	--	--
ALT or AST > 2 X Baseline AND > 3 x ULN AND accompanied by symptoms^b	
 • Discontinue study drug • Hospitalize if clinically appropriate • Establish causality and complete liver event checklist (in SOM) 	--	Continue monitoring Repeat tests ^a until resolution ^c	--	--

Criteria	First Action	Result	Second Action	Result	Third Action
ALT or AST > 2 X Baseline AND > 5 to \leq 8 x ULN	
 Repeat tests^a within 48 hours of notification of result HOLD study drug until repeat test results available Establish causality and complete liver event checklist (in SOM) 	↑	Part 1 
 Discontinue study drug 		
 Continue monitoring with Repeat tests^a 2-3 times per week until resolution ^c Update liver event checklist
			Part 2 
 Reduce dose (Table 6-1). Restart study drug at reduced dose Repeat tests^a 2-3 times a week after re-starting study drug Update liver event checklist (in SOM) 	↑	Part 2 If elevated after re-starting study drug, discontinue study drug 
 Continue monitoring with Repeat tests^a until resolution ^c Update liver event checklist
				↓	If values normalize, continue with reduced dose. 
 Repeat tests^a two and three weeks after re-starting study drug If levels remain \geq 2x Baseline 3 weeks after dose reduction, discontinue study drug 
 Continue monitoring with Repeat tests^a until resolution ^c Update liver event checklist

Criteria	First Action	Result	Second Action	Result	Third Action

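### Protocol 6.2.1 reduces the dose when a repeat confirms ALT and/or AST but keeps it when the repeat does not confirm ALT, so the conditions overlap when both enzymes triggered and only AST persists

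*Protocol*

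**What the plan says.** Protocol 6.2.1 sets out the Part 2 dose-reduction option. Entry to it is by either enzyme: "For patients who experience ALT or AST elevations meeting the definitions outlined in" Table 15-1 may have treatment interrupted or reduced, and "Patients with AST or ALT values meeting the requirement will be instructed to return to the clinic for an additional visit".

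Two consecutive paragraphs then act on the repeat result:

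- Reduce: "If the additional laboratory evaluation confirms the increase of ALT and/or AST values, the study treatment will be reduced to the next dose level".
- Keep: "If the additional laboratory evaluation does not confirm the significant increase of ALT values, the patient will continue with the assigned/original dose level".

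The rule for a persistent or second elevation on the reduced dose, in the same section, again names both enzymes: "If the repeat tests confirm the elevated ALT or AST values, the patient will discontinue study treatment". Only one reduction step is allowed, and a patient may not go back to the original dose.

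The section also refers to Table 15-1 (Appendix 1), which it says "outlines the required testing frequency and resultant actions dependent on the outcome of the repeat assessments". The rows of that table that can lead to a reduction are entered by either enzyme, for example "ALT or AST > 2 X Baseline AND > 5 to" 8 × ULN. The legend below the table counts an elevation as confirmed when it stays above 90% of the first raised level, and as decreasing at 90% or below. It does not limit either definition to ALT.

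On the analysis side, Protocol 11.4.2 and SAP 7.1.3 plan an additional Part 2 repeated-measures ANCOVA in which everything measured after a dose reduction is treated as missing.

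**The concern.** A rule that branches on a repeat test should give each result exactly one action. Here the reduce branch is defined on two enzymes and the keep branch on one, so a single result can satisfy both. Both branches are worded as mandatory.

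Two things are at stake. The first is that an explicit protocol sentence would keep a patient with a confirmed AST elevation on the assigned dose, while the sentence before it and Table 15-1 point the other way. The second is comparability of the data. Two sites with identical laboratory results could follow different sentences, so that one patient has a dose reduction and the other does not. Because returning to the original dose is barred, a decision to reduce cannot be reversed. It also removes that patient's later GGT values from the additional ANCOVA.

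**Working it through.** The plan gives no figure to reproduce. The check is to list every trigger and repeat result and apply both sentences of 6.2.1.

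**Inputs**

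- Reduce if ALT and/or AST is confirmed (6.2.1).
- Keep if ALT is not confirmed (6.2.1).
- Confirmed means above 90% of the first raised level (legend to Table 15-1).

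The keep sentence can be read in two ways. On the *literal* reading it applies whenever ALT is not confirmed. On the *narrow* reading it presupposes that ALT was significantly raised in the first place, so it is silent when only AST triggered.

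| Enzymes that met the trigger | Confirmed on repeat | Literal reading | Narrow reading |
|---|---|---|---|
| Both | Both | Reduce | Reduce |
| Both | ALT only | Reduce | Reduce |
| Both | AST only | **Reduce and keep** | **Reduce and keep** |
| Both | Neither | Keep | Keep |
| ALT only | ALT | Reduce | Reduce |
| ALT only | None | Keep | Keep |
| AST only | AST | **Reduce and keep** | Reduce |
| AST only | None | Keep | **No sentence in 6.2.1** |

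Each reading leaves two of the eight combinations defective. One of them, both enzymes raised and only AST persisting, is contradictory on either reading.

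**Illustration of that case.** The values are assumed: ULN 40 U/L for both enzymes, baseline ALT 50 and AST 45.

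- First result, ALT 230: 230/40 = 5.75 × ULN and 230/50 = 4.6 × baseline.
- First result, AST 230: 230/40 = 5.75 × ULN and 230/45 = 5.1 × baseline. Both enzymes meet the row for more than 2 × baseline and above 5 up to 8 × ULN.
- Repeat, ALT 80: 80/230 = 35%, which is not above 90%, so not confirmed.
- Repeat, AST 228: 228/230 = 99%, which is above 90%, so confirmed.

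The reduce sentence applies because AST is confirmed. The keep sentence applies because ALT is not.

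**Against Table 15-1.** Either enzyme is enough to enter the row, and the 90% rule is not tied to ALT, so a persisting AST counts as a confirmed elevation. The table has no branch that returns a patient to the assigned dose because ALT alone has fallen. The keep sentence therefore contradicts it in this case.

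**The case against.** The strongest reply is that the keep sentence speaks of the significant ALT increase, which presupposes that there was one. On that ordinary reading an AST-only trigger with AST confirmed receives a single instruction. This stands. A reader might infer from the wording that every confirmed AST-only elevation receives opposite instructions, and the documents support that only on the most literal reading. The reply does not reach the case where both enzymes triggered, and it leaves an unconfirmed AST-only trigger with no keep-dose sentence in 6.2.1 (Table 15-1 does supply an action there).

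A second reply is that Table 15-1 is the operating rule. Section 6.2.1 points to it and cannot be used without it: the section's own sequence omits, for example, the table's second repeat before a Part 2 reduction in the row up to 5 × ULN. A careful site may well settle the matter from the table. That lowers the risk, but no sentence says that the table prevails, and the disagreement between the two is itself the defect.

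Third, a reader might infer that such patients would be left unprotected. The documents do not support that. In the row above 5 to 8 × ULN, drug is held pending the repeat. After a restart, tests follow 2–3 times a week, with discontinuation if values are elevated. In the row up to 5 × ULN, drug is held in Part 2 after a first confirmed repeat. Symptomatic elevations and those above 8 × ULN have their own rules, which name both enzymes, and Protocol 7.1 requires stopping when the investigator believes that continuing would harm the patient.

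Fourth, the additional ANCOVA acts on reductions that actually happened, so it remains well defined whichever sentence a site follows. This also stands. The point is that the same laboratory result could lead to different data, not that the method fails.

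Finally, the reduction procedure is in the Site Operations Manual, which is not among the documents, so what sites are told in practice cannot be judged.

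**Conclusion.** The point holds in a limited form. The two branches of 6.2.1 are not mutually exclusive. They conflict on any reading when both enzymes met the trigger and only AST remains above 90% of its first level, and there the keep sentence also contradicts Table 15-1. For AST-only triggers there is either a conflict (literal reading) or a missing keep-dose sentence (narrow reading), but not both.

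The documents give no rate for AST persisting without ALT, so the number of patients affected cannot be estimated. The laboratory values in the illustration are assumptions and say nothing about frequency. Every parallel sentence in the section names both enzymes, so the likeliest explanation is a drafting omission. It is still worth correcting, because it sits in an operative hepatic-safety dosing rule and determines whether a reduction takes place.

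**What to change.** Reconcile the two sentences of 6.2.1 with each other and with Table 15-1. Confirmation and non-confirmation should refer to the same enzyme or enzymes that met the trigger, and no repeat result should satisfy both. The text should state explicitly what happens when both enzymes triggered and only one persists, and when an AST-only rise is not confirmed. Which action applies in each case is for the sponsor to state. It would also help to say whether 6.2.1 or Table 15-1 governs if they differ, and to check the Site Operations Manual against the corrected text.

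The cost is a short protocol correction and a note to sites. Sample size and planned analysis methods do not change.

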6.3 Treatment assignment

Randomization numbers will be assigned in ascending, sequential order to eligible subjects (see Site Operations Manual for details).

The randomization numbers will be generated using the following procedure to ensure that treatment assignment is unbiased and concealed from subjects and investigator staff.

In Part 1 a randomization list will be produced by or under the responsibility of Novartis Drug Supply Management using a validated system that automates the random assignment of treatment arms to randomization numbers in the specified ratio. The investigator will enter the randomization number on the CRF.

In Part 2 a subject randomization list will be produced by the IRT provider or by a delegate under their supervision, using a validated system that automates the random assignment of treatments to randomization numbers. These randomization numbers are linked to the different treatment arms.

In Part 2 randomization will be stratified by whether the patient is taking UDCA or not and the severity of pruritus.

Patients who participated in Part 1 may be enrolled in Part 2, provided they meet all the eligibility criteria. They will be assigned a new screening and randomization number. The screening number a subject had in Part 1 will be recorded as part of the CRF data collected for Part 2, if a subject participates in both parts.

The randomization scheme for all subjects will be reviewed and approved by a member of the Randomization Office.

6.4 Treatment blinding

This is a double-blind study: subjects, investigator staff (with the exception of unblinded pharmacy staff or authorized designee responsible for dispensing study medication), persons performing the assessments, and data analysts will remain blinded to the identity of study treatments.

The identity of the treatments will be concealed by the use of study drugs that are all identical in packaging, labeling, schedule of administration, appearance and odor. In Part 2, the blind for the different dose levels will be maintained through the use of a double-dummy design, with additional placebo capsules given in active treatment groups when needed to maintain the blind.

Randomization data are kept strictly confidential, and are accessible only to authorized personnel (unblinded pharmacist or authorized designee), until un-blinding of the trial as described in the table in the Blinding levels table in the Site Operations Manual.

The bioanalyst will request a copy of the randomization to facilitate analysis of the samples. The bioanalyst will provide the sample data to the team under blinded conditions. The bioanalyst will keep this information confidential until interim analysis (Part 1 only) or final clinical database lock.

Unblinding will only occur in the case of patient emergencies (see [Section 6.5](#)), at the time of the interim analysis and upon database lock, either at the conclusion of the study or completion of a Cohort or Part of the study.

Part 1

The sponsor will be unblinded and the randomization released to the CTT including the Modeler when the interim analysis is performed after subjects in a cohort have completed Day 28 of the study.

The Interim Analysis Team may communicate interim analysis results (e.g., dose escalation decision, evaluation of PoC criteria or information needed for planning/modifying another study) to relevant Novartis teams for information, consulting and/or decision purposes.

Cohorts in Part 1 may have their data cleaned and locked before the conclusion of the whole study. In event of database lock for a Cohort or Part of the study, treatment codes for the subjects included in the locked cohort or part will be released and the data may be disseminated.

Part 2

The sponsor will remain blinded to the identity of study treatments during the study. An unblinded interim analysis will be performed by a study independent statistician and programmer when approximately 40 patients have completed their Week 8 visit in Part 2. A selected Novartis team not involved in the clinical conduct of the study (DMC) will be unblinded to the Week 8 results and will advise on whether sample size adjustment is required (see [Section 11.8](#)).

6.5 Emergency breaking of assigned treatment code

Emergency un-blinding should only be undertaken when it is essential to treat the subject safely and efficaciously. Most often, study treatment discontinuation and knowledge of the possible treatment assignments are sufficient to treat a study subject who presents with an emergency condition.

In Part 1 a complete set of emergency code break cards will be provided to the investigator sites and a complete set will be available at Novartis. All code break cards must be retained until the end of the study and returned to Novartis. They must be stored in a secure place but be accessible in case of emergency. The investigator will receive a blinded code break card for each subject, with the details of drug treatment covered by a removable, scratch-off cover. In an emergency, the scratch-off cover can be removed to determine the treatment. The scratch-off covers are not to be removed for any reason other than an emergency. When the investigator removes the scratch-off cover he/she must note the date, time, and reason for removing it and retain this information with the case report form documentation. **The unblinded treatment code should not be recorded on the CRF.** The investigator must also immediately inform the Novartis local monitor that the code has been broken.

In Part 2 emergency treatment code breaks are performed using the IRT. When the investigator contacts the system to break a treatment code for a subject, he/she must provide the requested subject identifying information and confirm the necessity to break the treatment code for the subject. The investigator will then receive details of the investigational drug treatment for the specified subject and a fax or email confirming this information. The system will automatically inform the study monitor for the site and the Study Team that the code has been broken.

It is the investigator's responsibility to ensure that there is a procedure in place to allow access to the code break cards or IRT in case of emergency. If appropriate, the investigator will inform the subject how to contact his/her backup in cases of emergency when he/she is unavailable.

